2.2 Rationale

2.2.1 Study Rationale

The current clinical trial will be conducted to assess the effect of zoliflodacin on cardiac repolarization. Medicinal products that prolong cardiac repolarization may have a proarrhythmic effect and have been associated with a specific, potentially fatal polymorphic ventricular tachycardia termed torsade de pointes (TdP). This tachycardia is usually observed in the setting of a prolonged QT interval, is often initiated after extrasystolic pauses, and is identified by the continuously twisting appearance of the QRS complex in the 12-lead ECG recording. Additional risk factors associated with a potential predisposition to the proarrhythmic effect include cardiac disease, congenital Long QT Syndrome (LQTS), hypokalemia, hypomagnesemia, bradycardia, and concurrent administration of other medicinal products known to prolong the QT interval.

The QT interval, which represents ventricular recovery time, reflects the time between the depolarization of the first myocardial cells and the completion of repolarization of the last myocardial cells. Like ventricular refractoriness, it is influenced by the autonomic nervous system and changes in HR, and also by electrolyte disturbances and medications.^{14,15} The duration of the QT interval has prognostic implications in both healthy and diseased populations, with an abnormally prolonged QT interval becoming an increasingly accepted marker of risk for malignant ventricular tachyarrhythmias.¹⁶

There are a number of compounds in various therapeutic classes that have proarrhythmic potential, including, among others, imidazoles, psychotropic agents, antihistamines, and antibiotics.¹⁷ Of particular concern is concurrent administration of other medicinal products known to prolong the QT interval and/or that are metabolized by and compete for cytochrome P4503A4 (CYP3A4) enzymes. A partial list of drugs considered to be associated with high-risk of TdP when associated with QTc prolongation is presented in [Appendix E: A Partial List of Drugs Causing QTc Prolongation and Torsade de Pointes](#).

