- *Note 1: Prohibited medications include moderate or strong CYP3A4 inducers (per 6.6) and other drugs with known risk for QT prolongation and TdP (Appendix E and 17); antibiotics; injectable or oral antidiabetic drugs; anti-lipid drugs; immunosuppressive agents; immune modulators; oral corticosteroids; anti-neoplastic agents; any vaccine (licensed or investigational) except licensed influenza vaccine during the flu season, which is allowed up to 7 days before first dosing or 7 days after last dosing*
 - *Note 2: Allowed medications include: oral contraceptives; H1 antihistamines; all medications approved for control of intraocular pressure including topical ophthalmic non-selective β -blockers, such as betaxolol, carteolol, levobunolol, metipranolol, and timolol; topical/ intranasal corticosteroids; nonsteroidal anti-inflammatory drugs (NSAIDs); licensed influenza vaccine during the flu season, 7 days before first dosing or 7 days after last dosing*
- 17) Use of non-prescription medications, vitamins, herbs, or nutritional supplements within 15 days before first dosing or planned use during the trial unless approved by the study clinician
- *Note 1: Intake of nutritional supplements, juice, and herbal preparations or other foods or beverages that may affect the various drug-metabolizing enzymes and transporters (e.g., grapefruit, grapefruit juice, grapefruit-containing beverages, apple or orange juice, vegetables from the mustard green family [e.g., kale, broccoli, watercress, collard greens, kohlrabi, Brussels sprouts, mustard], and charbroiled meats) within 7 days before dosing*
 - *Note 2: Exceptions: St. John's wart is not allowed within 30 days of dosing; vitamins*

and over-the-counter (OTC) medications taken for a brief period (<48 h) for the treatment of common symptoms (such as headache, indigestion, muscle pain) may be allowed as approved by the designated study clinician

- 18) Intake of caffeinated beverages or food within 72 h before first dosing or a history of high caffeine consumption (e.g., in the last 4 months drinking >5 cups of coffee/day)
- 19) Smoking or use of tobacco or nicotine-containing products within 30 days before first dosing
- 20) Engagement in strenuous exercise within 15 days before first dosing (e.g., marathon running, long-distance cycling, weight lifting) and during the trial

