9.1.2. Prior and Concomitant Medications

All medications will be coded using the current version of the World Health Organization (WHO) Drug dictionary (WHO Drug Dictionary Enhanced C3 September 1, 2018 or higher). The use of prior and concomitant medications taken during the study will be summarized by treatment and by Anatomical Therapeutic Code ATC 1 and ATC 2 (separately in [Table 30](#) for prior medications and [Table 31](#) for

concomitant medications). Individual subject listings will be presented for all prior and concomitant medications (separately in [Listing 19](#) for prior medications and [Listing 20](#) for concomitant medications).

Drugs will be listed and summarized as prior medications when the end date for the medication is before the first dose of study product and listed and summarized as concomitant medications otherwise.

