14.4 Summary of Prior and Concomitant Medications

Table 30: Number and Percentage of Subjects with Prior Medications by WHO Drug Classification and Sequence

[Instruction: Include prior medications (medications with an end date prior to first dose) only.]

WHO Drug Code Level 1, Anatomic Group	WHO Drug Code Level 2, Therapeutic Subgroup	ABCD (N=X)	ACDB (N=X)	ADBC (N=X)	BADC (N=X)	BDCA (N=X)	BCAD (N=X)	CDAB (N=X)	CABD (N=X)	CBDA (N=X)	DCBA (N=X)	DBAC (N=X)	DACB (N=X)	All Subjects (N=X)
		n (%)												
Any Level 1 Codes	Any Level 2 Codes	x (x)												
[ATC Level 1 - 1]	Any [ATC 1 - 1]	x (x)												
	[ATC 2 - 1]	x (x)												
	[ATC 2 - 2]	x (x)												
	[ATC 2 - 3]	x (x)												
[ATC Level 1 - 2]	[ATC 2 - 1]	x (x)												
	[ATC 2 - 2]	x (x)												
	[ATC 2 - 3]	x (x)												

Treatment A = 2 g zoliflodacin; Treatment B = 4 g zoliflodacin; Treatment C = placebo; Treatment D = 400 mg moxifloxacin

Table 31: Number and Percentage of Subjects with Concomitant Medications by WHO Drug Classification and Treatment

[Instruction: Include concomitant medications (medications that are ongoing or that have an end date after first dose) only. The associated treatment for a concomitant medication should be the last treatment received prior to the start of the medication.]

WHO Drug Code Level 1, Anatomic Group	WHO Drug Code Level 2, Therapeutic Subgroup	2 g Zoliflodacin (N=X)	4 g Zoliflodacin (N=X)	Placebo (N=X)	400 mg Moxifloxacin (N=X)	Any Treatment (N=X)
		n (%)	n (%)	n (%)	n (%)	n (%)
Any Level 1 Codes	Any Level 2 Codes	x (x)	x (x)	x (x)	x (x)	x (x)
[ATC Level 1 - 1]	Any [ATC 1 - 1]	x (x)	x (x)	x (x)	x (x)	x (x)
	[ATC 2 - 1]	x (x)	x (x)	x (x)	x (x)	x (x)
	[ATC 2 - 2]	x (x)	x (x)	x (x)	x (x)	x (x)
	[ATC 2 - 3]	x (x)	x (x)	x (x)	x (x)	x (x)
[ATC Level 1 - 2]	[ATC 2 - 1]	x (x)	x (x)	x (x)	x (x)	x (x)
	[ATC 2 - 2]	x (x)	x (x)	x (x)	x (x)	x (x)
	[ATC 2 - 3]	x (x)	x (x)	x (x)	x (x)	x (x)

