16.2.10 Prior and Concomitant Medications**Listing 19: Prior Medications**

[Instruction: Include prior medications (medications with an end date prior to dosing) only. Listing will be sorted by Sequence, then by Subject ID, and then by CM Number. Medication start and end Days are relative to enrollment (Day 1). If start date is more than 30 days before enrollment then categorize as: 1-12 months prior to enrollment, 1-5 years prior to enrollment, or >5 years prior to enrollment.]

Sequence	Subject ID	CM Number	Medication	Medication Start Day	Medication End Day	Indication	Taken for a condition on Medical History? (MH Description; Number)	ATC Level 1 (ATC Level 2)
ABCD	PHU.0123	001	BENADRYL	1-12 months prior to enrollment	1-12 months prior to enrollment	ITCHING	No	DERMATOLOGICALS (ANTIPRURITICS, INCL. ANTIHISTAMINES, ANESTHETICS, ETC.)

Treatment A = 2 g zoliflodacin; Treatment B = 4 g zoliflodacin; Treatment C = placebo; Treatment D = 400 mg moxifloxacin

Listing 20: Concomitant Medications

[Instruction: Include concomitant medications (medications that are ongoing or that have an end date after dosing) only. Listing will be sorted by Sequence, then by Subject ID, and then by CM Number. Medication start and end Days are relative to enrollment (Day 1). If start date is more than 30 days before enrollment then categorize as: 1-12 months prior to enrollment, 1-5 years prior to enrollment, or >5 years prior to enrollment. If ongoing, display “Ongoing” in End Day column. The Treatment (Sequence) column should show the most recent treatment prior to the medication start day, with the sequence randomized to in parentheses. If the Medication Start Day is the same day zoliflodacin, moxifloxacin, or placebo is administered, then the Treatment will be the study product administered on the Medication Start Day.]

Treatment (Sequence)	Subject ID	CM Number	Medication	Medication Start Day	Medication End Day	Indication	Taken for an AE? (AE Description; Number)	Taken for a condition on Medical History? (MH Description; Number)	ATC Level 1 (ATC Level 2)
2 g zoliflodacin (ABCD)	PHU.0123	001	BENADRYL	2	2	ITCHING	Yes (MACULAR RASH; 001)	No	DERMATOLOGICALS (ANTIPRURITICS, INCL. ANTIHISTAMINES, ANESTHETICS, ETC.)

Treatment A = 2 g zoliflodacin; Treatment B = 4 g zoliflodacin; Treatment C = placebo; Treatment D = 400 mg moxifloxacin

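### SAP Table 31 books each concomitant drug only to the treatment that preceded its start, so its by-treatment counts misstate co-medication that began before dose 1 or spans periods

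*SAP*

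**What the plan says.** SAP 9.1.2 separates prior from concomitant drugs by end date alone: "Drugs will be listed and summarized as prior medications when the end date for the medication is before the first dose of study product", and they are "listed and summarized as concomitant medications otherwise". The Table 31 shell (SAP Appendix 1, section 14.4) accordingly takes in "medications that are ongoing or that have an end date after first dose". Drugs begun before the first dose and still being taken are therefore included. The shell has one column for each of the four treatments plus an Any Treatment column, and it fills the treatment columns by this rule: "The associated treatment for a concomitant medication should be the last treatment received prior to the start of the medication".

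Listing 20 (SAP Appendix 3, section 16.2.10) starts from a similar rule: "The Treatment (Sequence) column should show the most recent treatment prior to the medication start day, with the sequence randomized to in parentheses". It then adds an exception that Table 31 does not state: a drug whose start day is a dosing day is shown against that day's study product. Listing 20 also prints each drug's start day and its end day, or marks it as ongoing.

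SAP 3.3 starts each of Periods 2 to 4 at the check-in day, which is the day before dosing. Each of Periods 1 to 3 ends the day before the next check-in.

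The protocol permits continuing co-medication. Exclusion criterion 16, Note 2 in section 5.2 says: "Allowed medications include: oral contraceptives; H1 antihistamines; all medications approved for control of intraocular pressure". Topical or intranasal corticosteroids and NSAIDs are on the same list.

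**The concern.** Attribution by start date makes sense for an adverse event, where the question is what the subject had last received when the event began. For a co-medication the question is what else was on board while each study treatment was being assessed. That depends on the whole interval from start to stop.

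Table 31 is the natural place to look for that answer. SAP 9.1.2 and 9.9 both send concomitant medication to Table 31, and Table 30 covers prior medication by sequence. In a QT trial readers will look. Protocol 2.2.1 describes the drug classes that contain compounds with proarrhythmic potential as "including, among others, imidazoles, psychotropic agents, antihistamines, and antibiotics", while section 5.2 allows H1 antihistamines. At stake is whether the study report's by-treatment co-medication table means what its column headings say.

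**Working it through.** The plan states no figure on this point, so there is nothing to reproduce. The check applies the Table 31 rule to the randomization scheme and compares the result with true period overlap.

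**Inputs.** The 12 sequences come from Protocol section 4, Table 1 (also SAP 3.3), with 6 subjects each, so 12 × 6 = 72. Each treatment stands in each period position in 3 of the 12 sequences, that is 3 × 6 = 18 subjects. The illustration assumes that every subject takes one drug and continues it to the end of the trial. A start after dose *k* means after that dose and before the next check-in.

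**Formulas, per treatment column.** For a start after dose *k* (*k* = 1 to 4), the Table 31 rule counts 18 subjects, and true overlap is 18 × (5 − *k*). For a start before dose 1, no treatment precedes the drug, so the rule counts 0, and true overlap is 18 × 4 = 72.

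| Drug started, then continued | Table 31 rule | True overlap | Share counted |
|---|---|---|---|
| before dose 1 | 0 | 72 | 0/72 = 0% |
| after dose 1 | 18 | 72 | 18/72 = 25% |
| after dose 2 | 18 | 54 | 18/54 = 33% |
| after dose 3 | 18 | 36 | 18/36 = 50% |
| after dose 4 | 18 | 18 | 18/18 = 100% |

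In every row the four columns are equal, so the table is too low but not lopsided. Subjects in the first row would appear in Any Treatment at most.

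**An uneven case.** Suppose every subject starts a continuing drug after the placebo dose. The rule shows placebo 72 and each other treatment 0. Each other treatment follows placebo in 6 of the 12 sequences, so true overlap is placebo 72 and each other treatment 6 × 6 = 36. The table turns a 72 to 36 contrast into 72 to 0.

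**Check-in start.** Take sequence CABD and a drug begun at Period 2 check-in (overall Day 8 in Protocol 7.3) and still on board at the 2 g dose on Day 9. The last treatment received was placebo, so Table 31 adds one to placebo and none to 2 g. SAP 3.3 places Day 8 in Period 2, so overlap would add one to 2 g.

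**Dosing-day start.** Take sequence ABCD and a drug begun on the Period 2 dosing morning before the dose. Under Table 31 the last treatment received is 2 g. Under Listing 20's exception it is 4 g. The same record can therefore sit under different treatments in the two outputs.

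**The case against.** The strongest reply is that little is lost. Listing 20 gives sequence, start day and end day for every concomitant drug, and Listing 7 gives each dosing day and time, so overlap with any period can be rebuilt for each subject. Contraceptives also have their own dated display, Listing 26. This stands. A reader might infer that the balance of co-medication cannot be seen at all, but the documents do not support that. The defect is in the summary table.

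A second reply is that a drug taken through all four periods is on board under every treatment in the same subject, so the crossover balances it. This also stands: in the first two rows of the table the true overlap is 72 in every arm. Leaving such drugs out of the treatment columns hides use, not imbalance. Likewise, for most drugs that span periods the assigned treatment is right but incomplete. It is misplaced only when a drug starts between doses, as at check-in, and is still on board at the next dose.

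A third reply is consistency. SAP 3.3 ties post-dose records to the last treatment received and treats the next check-in as follow-up of the previous treatment. That is sound for a measurement taken at one moment before the next dose. It does not carry over to a drug that remains on board after it.

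A reader might also infer that hidden co-medication biases the placebo-corrected QTcF change. The documents do not show this. Protocol 6.6 bars drugs with torsade risk for 30 days before dosing and during the trial. Protocol Appendix E, a partial list, names no antihistamine and no ophthalmic beta-blocker. ECG SAP 5.3 takes a separate baseline in each period, so a drug already on board before dosing also enters that baseline. Table 31 feeds no QTcF model.

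Finally, start-date attribution has a use: it shows which drugs were newly started after each treatment and pairs with Listing 20's column on use for an adverse event. That is a reason to keep it in the listing.

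**Conclusion.** The point holds for Table 31, and it is minor. The stated rule leaves drugs continuing from before dose 1 without a treatment, counts multi-period drugs under one treatment only, books check-in starts to the previous treatment, and differs from Listing 20 for drugs started on a dosing day. Its columns therefore do not report co-medication by treatment.

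The percentages rest on the constructed case of one continuing drug in all 72 subjects. They measure how incomplete the rule is, not how many subjects will be affected. The documents give no expected number of users. The primary QTcF, assay-sensitivity and concentration-QTcF analyses are unaffected, as is the sample size.

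**What to change.** Change the Table 31 instruction so that a subject is counted once per ATC class under every treatment whose SAP 3.3 dosing period overlaps the drug's start-to-end interval, with ongoing drugs running to the end of that subject's participation. This places drugs continuing from before dose 1. It also puts check-in and dosing-day starts in the period to which SAP 3.3 assigns those days. Add a footnote that one drug may appear in several treatment columns.

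Keep start-date attribution in Listing 20, so that newly started drugs remain visible, and footnote both displays to say that they answer different questions.

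The cost is shell wording, a simple date-overlap program and the footnotes. Start and end days are already planned output. The trade-off is that Table 31 will no longer separate new from continuing use, which Listing 20 still does.

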14.5 Tolerability

Table 32: Assessment of Tolerability

	All Subjects (N=X)	
	n	%
Tolerability to zoliflodacin		
Subject did not discontinue study drug due to AE		
Subject did not choose to withdraw from the study due to an AE		
Subject was not withdrawn from the study due to an AE		

Note: Tolerability was concluded for a subject unless any one of the following occurred after receipt of a dose of zoliflodacin: 1) subject discontinued study drug due to an AE, 2) subject choose to withdraw from the study due to an AE at any time from first receipt of zoliflodacin until end of study, or 3) subject was withdrawn from the study by the investigator due to an adverse event at any time from first receipt of zoliflodacin until end of study

N = Number of subjects in the Safety Population who received a dose of zoliflodacin

14.6 Pharmacokinetics**Table 33: Summary Statistics for Zoliflodacin Concentrations by Nominal Time, after Single 2 g Zoliflodacin Dose**

Subject ID	Zoliflodacin Concentration (ng/mL) by Nominal Time ^a After Dose (h)									
	0	0.5	1	2	3	4	6	8	12	24
PHU.00101	x	x	x	x	x	x	X	x	x	x
PHU.00102	x	x	x	x	x	x	X	x	x	x
PHU.00102	x	x	x	x	x	x	X	x	x	x
...	x	x	x	x	x	x	X	x	x	x
Statistics	x	x	x	x	x	x	X	x	x	x
N ^b	x	x	x	x	x	x	X	x	x	x
Mean	x	x	x	x	x	x	X	x	x	x
SD	x	x	x	x	x	x	X	x	x	x
Min	x	x	x	x	x	x	X	x	x	x
Median	x	x	x	x	x	x	X	x	x	x
Max	x	x	x	x	x	x	X	x	x	x
CV%	x	x	x	x	x	x	X	x	x	x
GM	x	x	x	x	x	x	X	x	x	x
GSD	x	x	x	x	x	x	X	x	x	x

^a Times are relative to time of dosing.

^b Number of data points used to compute the summary statistics. For calculation of summary statistics, BQL values were imputed as 0 if they did not come after a PK sample concentration that is above the LLOQ and treated as missing otherwise.

Table 34: Summary Statistics for Zoliflodacin Concentrations by Nominal Time, after Single 4 g Zoliflodacin Dose

This table will repeat Table 32 for zoliflodacin concentrations after a single 4 g zoliflodacin dose.

Table 35: Summary Statistics for Zoliflodacin PK Parameters, after Single 2 g Zoliflodacin Dose

Statistic	C _{max} (ng/mL)	T _{max} (h)	T _{last} (h)	AUC _(0-last) (h*ng/mL)	AUC _(0-inf) (h*ng/mL)	K _e (/h)	t _{1/2} (h)	CL/F (L/h)	V _z /F (L)
N	x	x	x	x	x	X	x	x	x
Mean	x	x	x	x	x	X	x	x	x
SD	x	x	x	x	x	X	x	x	x
Min	x	x	x	x	x	X	x	x	x
Median	x	x	x	x	x	X	x	x	x
Max	x	x	x	x	x	X	x	x	x
CV%	x	x	x	x	x	X	x	x	x
GM	x	x	x	x	x	X	x	x	x
GSD	x	x	x	x	x	X	x	x	x

Table 36: Summary Statistics for Zoliflodacin PK Parameters, after Single 4 g Zoliflodacin Dose

This table will repeat Table 34 for zoliflodacin PK parameters after a single 4 g zoliflodacin dose.
--

Table 37: Summary Statistics for Zoliflodacin Exposure Measure Ratios Comparing a Single 4 g Oral Dose to a Single 2 g Oral Dose

Statistic	C_{max} Ratio	AUC_(0-last) Ratio	AUC_(0-inf) Ratio
N	x	X	x
Min	x	X	x
Median	x	X	x
Max	x	X	x
CV%	x	X	x
GM	x	X	x
95% CI	(x, x)	(x, x)	(x, x)

10.1 Disposition of Subjects

9.1 Overall Study Design and Plan Description

Figure 1: Study Design

[figure not shown]
NOTE: A, B, C, and D refer to each of the study treatments: Treatment A = 2 g zoliflodacin; Treatment B = 4 g zoliflodacin; Treatment C = placebo; Treatment D = 400 mg moxifloxacin. This is a four-treatment, four-period, crossover trial. Treatments and treatment sequences will be randomized using a 12-sequence design balanced for period and first-order carryover effects, and double-blinded, except for administration of moxifloxacin. Six subjects will be randomized to each treatment sequence. The schematic displays only two of the 12 sequences.

* See Section 3.3 for details and a complete list of planned treatment sequences.

Figure 2: Study Flow Diagram

[Implementation Note: In the SAP, include a blank diagram with the possible reasons why subjects may be excluded from analyses. The reasons for exclusion should be in line with the SAP text. If possible, indicate the analysis population in the CONSORT diagram. Order the reasons for exclusion by descending ‘N’ or ‘n’].

The below mockup for the flow diagram is preliminary. The flow diagram will show the number of subjects screened and enrolled, the reasons for screening failures, the number of subjects completing each period by sequence, and reasons for early termination or exclusion from the primary analysis.

14.3.1.2 Unsolicited Adverse Events

Figure 3: Frequency of Related Adverse Events by MedDRA System Organ Class and Severity, Any Time after First Dose

[Implementation Note: This figure includes serious and non-serious unsolicited adverse events deemed related to study product. Instead of “Group A”, report figure will say “Any Time After First Dose” at the top of the figure. Figure will be repeated for each dose group. Note that this figure will present total counts of adverse events, and a subject may be represented by more than one count for the same type of adverse event.]

[figure not shown]

Figure 4: Frequency of Related Adverse Events by MedDRA System Organ Class and Severity, after 2 g Zoliflodacin and Prior to Next Dose

This figure will repeat Figure 4 for AEs occurring after 2 g Zoliflodacin.

Figure 5: Frequency of Related Adverse Events by MedDRA System Organ Class and Severity, after 4 g Zoliflodacin and Prior to Next Dose

This figure will repeat Figure 4 for AEs occurring after 4 g Zoliflodacin.

Figure 6: Frequency of Related Adverse Events by MedDRA System Organ Class and Severity, after Placebo and Prior to Next Dose

This figure will repeat Figure 4 for AEs occurring after Placebo.

Figure 7: Frequency of Related Adverse Events by MedDRA System Organ Class and Severity, after 400 mg Moxifloxacin and Prior to Next Dose

This figure will repeat Figure 4 for AEs occurring after 400 mg Moxifloxacin

Figure 8: Incidence of Related Adverse Events by MedDRA System Organ Class and Maximum Severity, Any Time after First Dose

[Implementation Note: This figure includes serious and non-serious unsolicited adverse events deemed related to study product. Instead of “Group A”, report figure will say “Any Time After First Dose” at the top of the figure. Figure will be repeated for each dose group. Note that this figure will present the number of subjects with types of adverse events, and a subject may not be counted more than once for the same type of adverse event, but will be counted only once for the maximum severity of the respective type.]

[figure not shown]

Figure 9: Incidence of Related Adverse Events by MedDRA System Organ Class and Severity, after 2 g Zoliflodacin and Prior to Next Dose

This figure will repeat Figure 8 for AEs occurring after 2 g Zoliflodacin.

Figure 10: Incidence of Related Adverse Events by MedDRA System Organ Class and Severity, after 4 g Zoliflodacin and Prior to Next Dose

This figure will repeat Figure 8 for AEs occurring after 4 g Zoliflodacin.

Figure 11: Incidence of Related Adverse Events by MedDRA System Organ Class and Severity, after Placebo and Prior to Next Dose

This figure will repeat Figure 8 for AEs occurring after Placebo.

Figure 12: Incidence of Related Adverse Events by MedDRA System Organ Class and Severity, after 400 mg Moxifloxacin and Prior to Next Dose

This figure will repeat Figure 8 for AEs occurring after 400 mg Moxifloxacin.

